5.4 Treatment overdose

No maximum tolerated dose was reached in dose escalation studies of pazopanib administered as a single agent at doses of up to 2000 mg/day. Pazopanib exposure at higher doses appeared to reach a plateau level at a dose of 800 mg daily. In the event of overdose (defined as administration of more than the protocol-specified dose), investigators should contact the Sponsor's appointed CRO and additional monitoring of the subject for AEs/SAEs and laboratory abnormalities should be considered. Decisions regarding dose interruptions or modifications will be discussed by the investigator in consultation with the Sponsor's coordinating investigators based on the clinical evaluation of the patient. Information regarding the quantity of the excess dose should be documented in the e-CRF.

5.5 Concomitant medications

All patients will be requested to provide a complete list of prescription and medications that have been taken within 4 weeks prior to screening. Investigators must be informed as soon as possible about any new medication(s) taken from the time of screening until the completion of the post-treatment follow-up visit. All concomitant medications taken during the study will be recorded in the electronic case report form (e-CRF) including indication, dose information, and dates of administration. If future changes are made to the list of permitted/prohibited medications, formal documentation will be provided and stored in the study file. Any such changes will be communicated to the investigative sites in the form of a letter.

No initial dose reduction permitted

Concomitant medications and non-drug therapies

Please refer to current Investigator's Brochure for list of concomitant and permitted medications.

Permitted Medications

All subjects will be asked to provide a complete list of prescription and over-the-counter medications that have been taken within the 4 weeks prior to Screening. The investigator must be informed as soon as possible about any new medication(s) taken from the time of Screening until the completion of the post-treatment follow-up visit.

All concomitant medications taken during the study will be recorded in the electronic case report form (e-CRF) with indication, dose information, and dates of administration.

Subjects should receive full supportive care during the study, including transfusion of blood and blood products, and treatment with antibiotics, analgesics, erythropoietin, or bisphosphonates, when appropriate.

Anti-emetics (such as prochlorperazine, lorazepam, ondansetron or other 5-HT antagonists) may be administered prophylactically in the event of nausea. Anti-diarrheals, such as loperamide, may be administered as needed in the event of diarrhea. Although acetaminophen at doses of ≤ 2 g/day is permitted, it should be used with caution in subjects with impaired liver function.

Permitted Medications – Use with Caution

Specific Recommendations Regarding Anticoagulants

Results from drug-drug interaction studies conducted in subjects with cancer suggest that pazopanib has no effect on the metabolism of S-warfarin. Hemorrhagic events, however, have been reported in clinical studies with pazopanib; therefore, pazopanib should be used with caution in subjects with increased risk of severe bleeding or who are receiving concomitant anticoagulant therapy (e.g., warfarin or its derivatives, low molecular weight heparin, unfractionated heparin). Subjects taking concomitant anticoagulant therapy should be monitored regularly for changes in relevant coagulation parameters as clinically indicated, as well as for any clinical bleeding episodes.

Specific Recommendations Regarding Hypoglycemic Therapy Including Insulin

Results from drug-drug interaction studies conducted in subjects with cancer suggest that there will be no clinically relevant pharmacokinetic interaction between pazopanib and hypoglycemic agents. Transient decreases in serum glucose (mainly Grade 1 and 2, rarely Grade 3) have been observed in clinical studies with pazopanib. In addition, decreases in blood sugar have been recently reported in subjects treated with another small molecule tyrosine kinase inhibitor, sunitinib (Billemont, 2008). Such changes may require an adjustment in the dose of hypoglycemic and/or insulin therapy. Subjects should be advised to report symptoms of hypoglycemia (e.g., confusion, visual disturbances, palpitations, sweating). Serum glucose should be tested during treatment with pazopanib as outlined in the protocol and as clinically indicated.

Specific Recommendations Regarding the Use of Simvastatin and Other Statins

Concomitant use of pazopanib and simvastatin increases the risk of ALT elevations. If a patient receiving concomitant simvastatin develops ALT elevations, follow guidelines for pazopanib dose modification and discontinue simvastatin. Insufficient data are available to assess the risk of concomitant administration of alternative statins and pazopanib.

The Effects of Pazopanib on Other Drugs

In vitro data indicate that pazopanib is a potential inhibitor for CYP3A4, CYP2C8, CYP2D6, CYP1A2, CYP2C9, CYP2C19, CYP2A6, CYP2B6, and CYP2E1. Pregnane X receptor transient transfection assay suggested some potential for human CYP3A4 induction at high concentrations. Results from drug-drug interaction studies conducted in subjects with cancer suggest that pazopanib is a weak inhibitor of CYP3A4, CYP2C8, and CYP2D6 *in vivo*, but had no clinically relevant effect on CYP1A2, CYP2C9 or CYP2C19 metabolism. Therefore, concomitant use of pazopanib with certain medications (substrates of CYP3A4, CYP2C8, and CYP2D6) with a narrow therapeutic window should be undertaken with **CAUTION** due to the potential for alterations in the pharmacologic effects of these medications or an increased risk for serious or life threatening adverse events associated with such medications (see below) secondary to the inhibition of specific CYP enzymes by pazopanib. In addition, the potential for drug interaction with such medications, although diminished, may persist after the last dose of pazopanib due to its long half-life (i.e., mean 30.9 hours); therefore, continue to exercise **CAUTION** for at least 7 days and up to 15 days after the last dose of pazopanib when administering these medications. These medications include (but are not limited to):

- Ergot derivatives: dihydroergotamine, ergonovine, ergotamine, methylergonovine (potential increased risk for developing ergot toxicity that includes severe vasospasm leading to peripheral as well as cerebral ischemia)
- Neuroleptics: pimozide (potential increased risk for QT interval prolongation, ventricular arrhythmia, and sudden death)
- Antiarrhythmics: bepridil, flecainide, lidocaine, mexiletine, amiodarone, quinidine, propafenone (potential increased risk for QT interval prolongation and Torsade de Pointes)
- Immune modulators: cyclosporine, tacrolimus, sirolimus (potential increased risk for nephrotoxicity and neurotoxicity)
- Miscellaneous: quetiapine, risperidone, clozapine, atomoxetine.

The Effects of Other Drugs on Pazopanib

Results from *in vitro* studies suggest that the oxidative metabolism of pazopanib in human liver microsomes is mediated primarily by CYP3A4, with minor contributions from CYP1A2 and CYP2C8. Furthermore, *in vitro* data suggest that pazopanib is a substrate for p-glycoprotein. Substances that induce or inhibit CYP3A4 may alter the pharmacologic effects of pazopanib and should be used with **CAUTION**.

Medications that inhibit CYP3A4 may result in increased plasma pazopanib concentrations. Co-administration of strong CYP3A4 inhibitors is prohibited (see Section on Prohibited Medications); therefore selection of an alternate concomitant medication with no or minimal potential to inhibit CYP3A4 is recommended.

CYP3A4 inducers may decrease plasma pazopanib concentrations. Selection of an alternate concomitant medication with no or minimal enzyme induction potential is recommended. **Drugs that induce CYP3A4 and may decrease pazopanib plasma concentrations include (but are not limited to):**

- Glucocorticoids: cortisone (>50 mg), hydrocortisone (>40 mg), prednisone (>10 mg), methylprednisolone (>8 mg), dexamethasone (>1.5 mg)
- Anticonvulsants: phenytoin, carbamazepine, phenobarbital, oxcarbazepine
- HIV antivirals: efavirenz, nevirapine
- Antibiotics: rifampin (rifampicin), rifabutin, rifapentene
- Miscellaneous: St. John's Wort, modafinil, pioglitazone

Prohibited Medications

Subjects should not receive other anti-cancer therapy [cytotoxic, biologic, radiation, or hormonal (other than leuprolide or other GnRH agonists)] while on treatment in this study.

Medications that inhibit CYP3A4 may result in increased plasma pazopanib concentrations; therefore, co-administration of strong CYP3A4 inhibitors is **PROHIBITED** beginning **14** days prior to the first dose of study drug until discontinuation from the study. **Strong CYP3A4 inhibitors include (but are not limited to):**

- Antibiotics: clarithromycin, telithromycin, troleandomycin
- HIV: protease inhibitors (ritonavir, indinavir, saquinavir, nelfinavir, lopinavir)
- Antifungals: itraconazole, ketoconazole, voriconazole
- Antidepressants: nefazodone

The time period that subjects should not receive any other investigational drugs prior to the first dose of study drug should be specified in the eligibility criteria.

The time period that subjects should not receive any other investigation drugs after receiving the last dose of study drug will depend on the objectives and endpoints of each particular study as well as whether pazopanib is being administered in combination with drugs with longer half-lives. In general, as far as pazopanib is concerned, subjects should not receive any other investigational drug within 15 days of the last dose of pazopanib and until post-treatment blood draws are completed.

5.6 Supportive care guidelines for diarrhea, nausea and vomiting

These general guidelines are provided to facilitate subject care in the event of diarrhea, thereby avoiding serious complications. Guidelines such as these should never replace sound clinical judgment. Experience thus far suggests that use of monotherapy pazopanib is associated with an increased incidence of diarrhea, primarily of Grade 1 or 2. In rare cases, diarrhea can be debilitating and potentially life threatening, with dehydration, renal insufficiency, and electrolyte imbalances.

Standardized and universal guidelines have been developed by an American Society of Clinical Oncology panel for treating chemotherapy-induced diarrhea [Benson, 2004].

Early identification and intervention is critical for the optimal management of diarrhea. A subject's baseline bowel patterns should be established so that changes in patterns while on treatment can be identified. An assessment of frequency, consistency, and duration of diarrhea, as well as knowledge of other symptoms such as fever, cramping, abdominal pain, nausea, vomiting, dizziness and thirst should be taken at baseline, permitting identification of patients at high risk of diarrhea. Patients should be educated on signs and symptoms of diarrhea with instructions to report any changes in bowel patterns to the study site physician.

The NCI CTCAE Version 4.0 criteria for defining diarrhea are provided below.

Table 4: NCI CTCAE Version 4.0 Criteria for Defining Diarrhea

Toxicity Grade	Diarrhea (includes diarrhea of small bowel or colonic origin and/or ostomy diarrhea)
1	Increase of <4 stools/day over baseline; mild increase in ostomy output compared to baseline
2	Increase of 4-6 stools/day over baseline; moderate increase in ostomy output compared to baseline
3	Increase of ≥7 stools/day over baseline; incontinence; hospitalization indicated; severe increase in ostomy output compared to baseline; limiting self-care activities of daily living
4	Life threatening consequences, urgent intervention indicated
5	Death

Uncomplicated diarrhea is considered mild to moderate and is defined as CTCAE Grade 1 to 2 with no complicating signs or symptoms.

Complicated diarrhea is severe and defined as CTCAE Grade 3 or 4 or Grade 1 or 2 with one or more of the following signs or symptoms: severe cramping, \geq Grade 2 nausea/vomiting, decreased performance status, fever, sepsis, Grade 3 or 4 neutropenia, obvious bleeding, dehydration.

Management Guidelines

Uncomplicated diarrhea of CTCAE Grade 1 or 2

- Hydration: have subject drink 8 to 10 large glasses (approximately 2 liters) of clear non-caffeinated liquids a day (e.g., broth or electrolyte-containing sports drinks).
- If Grade 2 diarrhea, consider dose reduction of investigational products.
- Dietary modifications: have subject stop all lactose-containing products and eat frequent, small meals
- Pharmacologic intervention using loperamide:
 - Begin loperamide at initial dose of 4 mg followed by 2 mg every 4 hours or after every unformed stool. The recommended maximum daily dose of loperamide is 16 mg/day.
 - Continuation of loperamide is suggested until diarrhea-free for 12 hours.
 - If mild to moderate diarrhea persists for more than 24 hours, administer loperamide 2 mg every 2 hours and pursue evaluation for other treatable causes.
 - If mild to moderate diarrhea persists after 48 hours total treatment with loperamide, discontinue study drug(s) and consider initiation of second-line agents (lomotil, octreotide).

Complicated diarrhea of CTCAE Grade 3 or 4 diarrhea or Grade 1 or 2 with complicating features requires aggressive management

- Subject must call study site physician immediately in response to any event of severe diarrhea with or without complications as listed above.
- Hospitalization may be required for subjects most at risk for life-threatening complications.
- Interrupt investigational products until symptoms resolve; consider reintroducing at a reduced dose (discuss with GSK Medical Monitor or designee).
- If loperamide has not been initiated, begin loperamide usage immediately at an initial dose of 4 mg followed by 2 mg every 2 hours or after every unformed stool. The recommended maximum daily dose of loperamide is 16 mg/day.
- If no improvement in severity after 24-hours of maximal loperamide dosing, subject must visit study site and be evaluated.
- For dehydration, use intravenous fluids as appropriate.
- Antibiotic therapy should be considered in patients, who present with signs and symptoms of bacterial diarrhea such as fever, bloody diarrhea, and presence of fecal leukocytes. Investigators should have a low threshold to start such treatment in patients with Grade 3 or Grade 4 neutropenia.
- Before initiation of antimicrobial therapy, stool cultures should be obtained. When bacterial etiology for diarrhea is suspected, study-treatment and anti-motility agents (loperamide or others) should be held.
- Intervention should be continued until diarrhea free for 24 hours.

Alternative pharmacologic intervention for uncomplicated and complicated diarrhea

- Lomotil (dephenoxylate 2.5 mg + atropine 0.025 mg) can be used. The recommended dose is 2 tablets 4 times daily. When diarrhea is under control, a dose reduction should be attempted.
- The synthetic octapeptide, octreotide, has been shown to be effective in the control of diarrhea induced by flouropyrimidine-based chemotherapy regimens when administered as an escalating dose by continuous infusion or subcutaneous injection. Octreotide can be administered at doses ranging from 100 μ g twice daily to 500 μ g 3 times daily, with a maximum-tolerated dose of 2000 μ g 3 times daily in a 5-day regimen.

Nausea and vomiting

Every attempt should be made to control nausea and vomiting in subjects who have emesis and are unable to retain pazopanib.

Routine pre-medication for nausea is not necessary, but symptomatic subjects should be treated with standard anti-nausea/anti-emetic therapy as necessary.

If a subject vomits after taking study medication, the subject should be instructed not to take a replacement dose on that same day. The subject should resume taking pazopanib at the next scheduled dose on the following day. If vomiting persists, then the subject should contact their physician.

To prevent or treat nausea and vomiting standard medications are recommended. Depending upon approved medications in your region, these may include: 5-HT₃ receptor antagonist (granisetron, ondansetron, dolasetron mesylate); NK-1 receptor antagonists such as aprepitant, metoclopramide, phenothiazines (prochlorperazine); corticosteroids, (dexamethasones, prednisone); and cannabinoids (dronabinol).

Reference:

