Grade 2 or 3, if clinically significant	Step 1. Interrupt IMP until toxicity resolves to ≤ Grade 1. Step 2. Restart IMP dose-reduced by 200 mg and monitor as clinically indicated.
Grade 4	Discontinue IMP and continue follow-up per protocol.

a. Well-controlled BP defined as SBP <140 mmHg and mean DBP <90 mmHg.

b. AEs are graded according to NCI Common Terminology Criteria for Adverse Events v4.0 (NCI CTCAE v4.0)

Abbreviations: BP, blood pressure; IMP, investigational medicinal product.

Dose Modifications and Management of Liver toxicity

Recommendations for IMP dose interruptions/modifications in case of liver-related treatment-emergent AEs are provided in the table below. As a general rule, since many subjects are taking multiple concurrent medications, it is critical to (a) do a thorough evaluation of the subject's concurrent medications (and ensure all are recorded in the e-CRF), and (b) identify and discontinue those with known hepatotoxicity and replace with a non-hepatotoxic equivalent for the same indication if necessary. Record alcohol use on appropriate

forms. Liver dysfunction must be fully evaluated even if clinical signs and symptoms indicate progression of liver tumor lesions. Imaging studies must be obtained to document potential progression of malignancy.

Table 3: Guidelines for Management of Treatment Emergent Hepatotoxicity

Event	Dose Modification Algorithms
(A). ALT of ≤ 3.0 x ULN	Continue pazopanib at current dose with full panel LFTs ^a monitored as per protocol.
(B). ALT >3.0 x ULN to ≤ 8.0 x ULN without bilirubin elevation (defined as total bilirubin ^b <2.0 x ULN or direct bilirubin $\leq 35\%$) and without hypersensitivity symptoms (e.g., fever, rash)	
Liver Event Monitoring Criteria:
 
(1) Continue pazopanib at current dose levels.
 
(2) Monitor subject closely for clinical signs and symptoms; perform full panel LFTs^a weekly or more frequently if clinically indicated until ALT/AST is reduced to Grade 1.

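### Section 5.6's two-hourly loperamide schedule cannot be kept for 24 hours under its own 16 mg/day maximum, and its study-drug actions for diarrhea do not match Table 2

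*Protocol*

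**What the plan says.** **Loperamide (Protocol section 5.6, management guidelines).**

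- Uncomplicated Grade 1-2 diarrhea, start: "Begin loperamide at initial dose of 4 mg followed by 2 mg every 4 hours or after every unformed stool". The limit is then given: "The recommended maximum daily dose of loperamide is 16 mg/day".
- Uncomplicated diarrhea, escalation once it has lasted more than 24 hours: "administer loperamide 2 mg every 2 hours and pursue evaluation for other treatable causes". The limit is not repeated in this bullet.
- Complicated diarrhea (Grade 3-4, or Grade 1-2 with complicating features): "begin loperamide usage immediately at an initial dose of 4 mg followed by 2 mg every 2 hours or after every unformed stool". The same 16 mg/day limit is the next sentence.

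**Study drug, section 5.6.** For uncomplicated Grade 2, the investigator is to consider a dose reduction. For uncomplicated diarrhea that does not settle: "If mild to moderate diarrhea persists after 48 hours total treatment with loperamide, discontinue study drug(s". For complicated diarrhea: "Interrupt investigational products until symptoms resolve; consider reintroducing at a reduced dose", after discussion with the medical monitor.

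**Study drug, section 5.3, Table 2.** Table 2 has no diarrhea row. The only row that can apply is the residual one for other clinically significant adverse events. It says to continue at Grade 1. At Grade 2 or 3, if clinically significant, it says to interrupt until Grade 1 or lower and restart reduced by 200 mg. At Grade 4 it says: "Discontinue IMP and continue follow-up per protocol".

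**Terminology, section 4.3.** A temporary interruption because of an adverse event is expressly distinguished from permanent discontinuation.

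**The concern.** A site reading section 5.6 meets a dosing interval and a daily limit that cannot both be met around the clock, with no statement of which gives way. The ambiguity carries into a later instruction. In the complicated branch, a site visit is required if there is no improvement after 24 hours of maximal loperamide, and what counts as maximal depends on whether the interval or the 16 mg figure governs.

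For the study drug, two sites with the same event can act differently according to the section they open. The protocol itself says that pazopanib monotherapy increases diarrhea, mainly Grade 1 or 2, so the escalation and 48-hour rules address the expected presentation. At Grade 4 the difference between stopping and possible reintroduction is a patient-safety matter. For the data, exposure and discontinuation counts would partly reflect which section was followed. A patient stopped early could also leave the per-protocol set, which section 11.4 limits to those with at least 3 weeks of treatment.

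**Working it through.** **Loperamide.** All inputs come from section 5.6: maximum 16 mg/day; initial dose 4 mg; later doses 2 mg; interval 4 hours or 2 hours. Daily dose = 2 mg x (24 / interval in hours). On a first day with the initial dose, 4 mg replaces the dose at hour 0. The dose at hour 24 is counted to the next day. The figures use the clock-based interval, not the alternative of dosing after each unformed stool.

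1. Four-hourly, first day: 4 + 5 x 2 = 14 mg. Later days: 6 x 2 = 12 mg. Both are within 16 mg, so the stated maximum fits the starting schedule.
2. Two-hourly escalation, uncomplicated diarrhea: 12 x 2 = 24 mg per 24 hours. 24 / 16 = 1.50, so 8 mg or 50% above the maximum. This step begins only after more than 24 hours of diarrhea, and the bullet states no initial dose.
3. Two-hourly, complicated branch, first day: 4 + 11 x 2 = 26 mg. 26 / 16 = 1.625, about 63% above. Later days: 24 mg, 50% above.
4. If the maximum is taken to cut the schedule short, the escalation reaches it with the eighth dose (8 x 2 = 16 mg, at hour 14). The complicated branch reaches it on its first day with the seventh dose (4 + 6 x 2 = 16 mg, at hour 12). Nothing further could be given that day, and the text mentions no such pause.

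Counting a dose at hour 24 changes step 1 to 16 mg and the first day of step 3 to 28 mg; the conclusion is the same.

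**Study-drug actions, section 5.6 against the residual row of Table 2.**

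- *Grade 4:* interrupt and consider reintroducing, against discontinue.
- *Grade 3:* interrupt and consider a reduced dose, against interrupt and restart reduced if clinically significant. These are broadly compatible.
- *Grade 2, uncomplicated:* consider a dose reduction, against interrupt and restart reduced if clinically significant.
- *Grade 1-2, uncomplicated, persisting after 48 hours of loperamide:* discontinue, permanence not stated, against continue at Grade 1 and interrupt at clinically significant Grade 2.

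**The case against.** The best defence on loperamide is that a limit and an interval are meant to be read together: dose every 2 hours up to the maximum. In the complicated branch the limit follows the schedule at once, which supports that reading. A reader might infer that the protocol instructs sites to exceed its own maximum. The documents do not support that. What stands is narrower: the interval cannot be kept for 24 hours under the limit, the text does not say that the limit truncates it, and the escalation bullet does not restate the limit. Nor does the 26 mg figure belong to that bullet; it arises only on the first day of the complicated branch.

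On the study drug, a reader might infer that milder diarrhea is punished more heavily than severe diarrhea. That is too strong, for two reasons.

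- The triggers differ. One rule needs persistence after 48 hours of loperamide; the other applies when complicated diarrhea presents.
- *Discontinue* in section 5.6 is not clearly permanent. Table 3 adds the word permanently for a recurrent liver event, and Table 2 adds continued follow-up; the diarrhea bullet has neither and goes on to second-line antidiarrheal agents. A temporary hold may have been meant. But section 4.3 separates the two concepts and Table 2 uses the two words for different actions, so the meaning needs stating.

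It can also be said that section 5.6, being specific to diarrhea, should override a residual row. That is reasonable, above all at Grade 1, but the protocol does not say so. Finally, section 5.6 calls itself general guidance that does not replace clinical judgment. This lowers the weight of the conflict without telling a site which instruction is the protocol's.

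**Conclusion.** The point holds as an inconsistency of moderate severity. The two-hourly schedule amounts to 24 mg per 24 hours against a stated 16 mg (50% over), or 26 mg on the first day of the complicated branch (about 63% over), assuming clock-based dosing through the full 24 hours. Section 5.6 and Table 2 give different study-drug actions at Grade 4, at Grade 2, and for persistent uncomplicated Grade 1-2 diarrhea. That comparison assumes that diarrhea falls under the residual row of Table 2; at Grade 2 it applies only to events judged clinically significant.

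Sample size, alpha and power are untouched. Any effect on the primary response endpoint should be limited: patients who stop for toxicity are still imaged every 8 weeks unless they start new anticancer therapy (sections 7.7 and 11.4), and the intent-to-treat analysis includes all participants. The effect on exposure and discontinuation counts cannot be sized from the protocol.

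**What to change.** The sponsor's clinical leads should:

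- reconcile both two-hourly loperamide schedules with the stated daily maximum, and say in each place how the two interact;
- state whether *discontinue* in section 5.6 means a temporary or a permanent stop, in the terms of section 4.3;
- align the section 5.6 study-drug actions with Table 2 grade by grade, or state which of the two governs diarrhea.

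No dose or clinical rule is proposed here. The cost is a text correction in an amendment and a letter to sites; no design element or analysis changes.
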